7.2. General Statistical Methods

All statistical analyses will be performed using the SAS System software, version 9.2 or later (Copyright[©] 2000 SAS Institute Inc., [name], USA. All rights reserved).

All statistical analyses will be conducted according to applicable Standard Operating Procedures, Work Instructions, and the study-specific statistical analysis plan.

Statistical models that account for censored data will be employed in appropriate circumstances (e.g., for time-to-event outcomes).

7.2.1. Analysis Sets

Endpoints will be analyzed on an intention-to-treat (ITT) basis and an implanted basis. For ITT analyses, all subjects who sign the IEC-approved study ICF and are enrolled in the study

will be included in the analysis, whether or not a study device was implanted. For implanted analyses, ITT subjects who had the study device implanted in the correct position during the index procedure will be included in the analysis.

7.2.2. Control of Systematic Error/Bias

To control for inter-observer variability, data from an independent core laboratory will be used for analysis at pre-specified time points. An independent CEC will adjudicate study endpoint related clinical events.

7.2.3. Number of Subjects per Investigative Center

A single center may enroll up to 25 subjects.

7.3. *Data Analyses*

Baseline and outcome variables will be summarized using descriptive statistics for continuous variables (mean, standard deviation, number of observations, minimum and maximum) and discrete variables (percentage and count/sample). Study endpoints are listed in Section 5.2.

Any changes to the planned statistical analyses made prior to performing the analyses will be documented in an amended statistical analysis plan approved before performing the analyses. Changes from the planned statistical methods after performing the analyses will be documented in the clinical study report along with a reason for the deviation.

8. Validation

The Global Clinical WI (BSC: 90702587): Clinical Data Reporting Validation will apply to all clinical data reports being generated per this document.

9. Programming Considerations

9.1. *Format of Output*

Results of analysis will be output programmatically to Microsoft Office® Word documents from SAS with no manual intervention. All output for the final statistical report will be in the form of a Word document containing tables, figures, graphs, and listings, as appropriate.

9.2. *Methods for Handling Missing Data*

All subjects who are enrolled will be eligible for evaluation, regardless of the treatment that ensues. Handling of dropouts and missing data will depend on their frequency and the nature of the outcome measure. Adjustments for missing outcomes data will be performed if deemed necessary to eliminate or minimize bias and will be described completely. Statistical models that account for censored data will be employed in appropriate circumstances, e.g.,

for time-to-event outcomes. Outlier values will be evaluated, and values determined to be invalid will be queried. All data will be included in the analysis unless judged to be invalid.

When calculating rates of adverse events, missing and partial dates will be handled as shown in the table below.

Partial Date	Action Taken
Entire adverse event onset date is missing	The procedure date will be used for the onset date.
The month and the day of the month are missing but the year is available	January 1 st will be used for the month and day of the onset date. However, if the imputed date falls before the procedure date, then the procedure date will be used for the onset date.
Day is missing, but the month and year are available	The 1 st will be used as the day of the onset date. However, if the imputed date falls before the procedure date, then the procedure date will be used for the onset date.

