Due to the addition of 25 more patients to the initial 25 patients implanted, the enrollment period will be extended to minimally 15 months; therefore, the total study duration from first subject enrolled to last subject follow-up is estimated to be at least 28 months.

The WATCHMAN FLX Pro CT study will be registered at www.ClinicalTrials.gov prior to enrollment of the first subject (see Section 22.1).

7.2. *Treatment Assignment*

Subjects who are identified by the investigators as having met all the inclusion and none of the exclusion criteria (see below **Table 8.2-1** and **Table 8.3-1**, respectively) may be treated with the WATCHMAN FLX Pro device.

7.3. *Justification for the Study Design*

In order to support the stated objectives of this study (see Section 6.1) while also limiting the potential exposure of study subjects to risk, approximately 50 subjects will be enrolled at 1 center. Device implantation will be done according to current indications and device labelling as described in the device IFU. Safety and effectiveness results will be reported on all enrolled subjects (see Section 18 for information on safety reporting). All subjects will be followed for up to 12 months post implant procedure. To decrease the risk of thrombotic or thromboembolic complications, subjects will be treated with single antiplatelet therapy (SAPT) for at least 3 months following WATCHMAN FLX Pro implantation.

8. Subject Selection

Eligibility for this study is determined per standard of care. Any subject who meets all the inclusion criteria, does not meet any of the exclusion criteria, and who provides written informed consent may be considered for enrollment in the study (see **Note 1** below). The subjects selected for participation may be from the Investigator's general patient population. The investigator has the responsibility for screening all potential subjects and selecting those who meet study inclusion criteria and do not meet any of the exclusion criteria as described below. All subjects will have unique identification numbers.

Vulnerable subjects (see **Table 25.2-1** for the definition of vulnerable subject) will not be enrolled in the WATCHMAN FLX Pro CT study.

8.1. *Study Population and Eligibility*

8.2. *Inclusion Criteria*

Subjects who meet all of the criteria in **Table 8.2-1** may be given consideration for inclusion in this clinical investigation, provided no exclusion criterion (see Section **8.3**) is met.

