11.2.3. Number of Subjects per Investigative Center

A single center may enroll up to 50 subjects.

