Study Design	WATCHMAN FLX™ Pro CT is a prospective, single-arm, single-center, premarket investigation to assess device tissue coverage in subjects with non-valvular atrial fibrillation (AF) who receive the WATCHMAN FLX Pro device to reduce the risk of stroke. Serial advanced imaging modalities such as CT and TEE will be used. A core laboratory will independently assess select results. A subject is considered enrolled in the study when the subject or the subject's legally authorized representative signs an Informed Consent Form (ICF) approved by the Independent Ethics Committee (IEC). Up to 25 subjects in whom placement of a WATCHMAN FLX Pro device is attempted will be enrolled. A baseline assessment including TEE and/or CT imaging with optional cardiac magnetic resonance imaging (MRI) will be done within 14 days prior to the implant procedure following core

A Pilot Study to Assess WATCHMAN FLX™ Pro Implants by Cardiac Computed Tomography, Magnetic Resonance Imaging and Transesophageal Echocardiography: WATCHMAN FLX™ Pro CT

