	
Note 3: Results are classified as no leak, leak >0 and $\leq 5\text{mm}$, or leak $>5\text{mm}$.
 
Note 4: TEE is required at 12 months if the 3-month TEE assessment suggests a leak $> 5\text{mm}$ or the 3-month CT assessment suggests a leak $> 3\text{mm}$; results must be sent to the core laboratory.
 
• 4D cardiac MRI flow analysis (if available) of the left atrium (LA) and LAA before and serially after device implant at 14 days, 45 days, and 3 months; data will be evaluated by an independent core lab• Changes compared to baseline in measures of biochemical markers including coagulation, platelet and endothelial activation and inflammation at 14 days, 45 days, and 3 months post implant procedure; correlations with morphological findings from imaging assessment of the device surface will be examined
a: Schulman S and Kearon C. J Thromb Haemost 2005;3:692-694Kaatz S, et al. J Thromb Haemost 2015;13:2119-26b: Bruno A, et al. Stroke 2011;42:2276-2279
Follow-up Schedule	Follow-up for all subjects will occur post-implant on the procedure day, at predischarge, and at 14 days, 45 days, 3 months, and 12 months post implant procedure. Follow-up will include clinical assessments at all time points and imaging assessments at 14 days, 45 days, and 3 months. Subjects who are enrolled but not implanted with a WATCHMAN FLX Pro device in the correct position will be followed for safety through 12 months after the initial attempted implant procedure by telephone or review of clinical files but will not undergo imaging assessments or evaluation of biochemical markers including measures of coagulation, platelet and endothelial activation and inflammation. The study will be considered complete after all available subjects have finished the 12-month follow-up visit.
Study Duration	Subjects will be followed for 12 months after the implant procedure. Enrollment is expected to take minimally 5 months; therefore, the total study duration from first subject enrolled to last subject follow-up is estimated to be at least 17 months.

A Pilot Study to Assess WATCHMAN FLX™ Pro Implants by Cardiac Computed Tomography, Magnetic Resonance Imaging and Transesophageal Echocardiography: WATCHMAN FLX™ Pro CT

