Statistical Hypothesis	There is no formal statistical hypothesis for this observational, single-arm study. No statistical inference will be made in the study.
Methods	Outcomes in the overall treatment cohort will be summarized using descriptive statistics for continuous variables (mean, standard deviation, number of observations, minimum and maximum) and discrete variables (percentage and count/sample).

3. Table of Contents

1. TITLE PAGE	1
2. PROTOCOL SYNOPSIS.....	2
3. TABLE OF CONTENTS.....	9
3.1. Table of Figures.....	10
3.2. Table of Tables	10
4. INTRODUCTION	11
5. STUDY OBJECTIVES AND ENDPOINTS.....	11
5.1. Study Objectives.....	11
5.2. Study Endpoints	11
5.3. Overview of Objectives and Endpoints	12
6. STUDY DESIGN	13
6.1. Scale and Duration.....	13
7. STATISTICAL CONSIDERATIONS	14
7.1. Endpoints	14
7.2. General Statistical Methods	14
7.2.1. Analysis Sets.....	14
7.2.2. Control of Systematic Error/Bias.....	15
7.2.3. Number of Subjects per Investigative Center	15
7.3. Data Analyses	15
8. VALIDATION	15
9. PROGRAMMING CONSIDERATIONS.....	15
9.1. Format of Output	15
9.2. Methods for Handling Missing Data	15
9.3. Rules and Definitions	16
9.4. Summarization of Site-Reported Serious and Non-Serious Adverse Events ..	16
10. BIBLIOGRAPHY.....	17

3.1. *Table of Figures*

Figure 4.1-1: WATCHMAN FLX Pro CT Study Design Overview 14

3.2. *Table of Tables*

Table 3.3-1: Overview of Objectives and Endpoints 13

4. Introduction

This statistical analysis plan (SAP) addresses the planned analyses for the clinical study entitled “A Pilot Study to Assess WATCHMAN FLX™ Pro Implants by Cardiac Computed Tomography, Magnetic Resonance Imaging and Transesophageal Echocardiography” (WATCHMAN FLX™ Pro CT). Approximately 25 consented subjects will be enrolled. Data for subjects receiving the WATCHMAN FLX Pro device will be collected over 12 months.

There is no formal statistical hypothesis for this observational, single-arm study.

5. Study Objectives and Endpoints

5.1. *Study Objectives*

The primary objective of this study is to measure device tissue coverage post-implantation of the WATCHMAN FLX™ Pro Left Atrial Appendage Closure (LAAC) Device (WATCHMAN FLX Pro) using the serial advanced imaging modalities of cardiac computed tomography (CT) and transesophageal echocardiography (TEE) and assess its relationship, if any, to clinical events.

5.2. *Study Endpoints*

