 - Device seal at 45 days post index implant procedure (see **Note 2**)
 - Device-related thrombus (including hypoattenuated thickening [HAT] per CT analysis)
 - Device surface morphology (inclusive of tissue coverage) post implant procedure as assessed over time

Note 2: Results are classified as no leak, leak > 0 and ≤ 5 mm, or leak > 5 mm

Note 3: TEE should be performed at 12 months if the 3-month TEE assessment suggests a leak > 5 mm or the 3-month CT assessment suggests a leak > 3 mm; results must be sent to the core laboratory.

- 4D MRI flow analysis (if available) of the left atrium (LA) and LAA before (7 days prior to the index procedure) and serially after device implant (at 14 days, 45 days, and 3 months); data will be evaluated by an independent core lab
- Changes compared to baseline in measures of biochemical markers including coagulation, platelet and endothelial activation and inflammation over time post implant procedure (at 14 days, 45 days, and 3 months); correlations with morphological findings from imaging assessment of the device surface will be examined

5.3. *Overview of Objectives and Endpoints*

Table 5.3-1 provides an overview of the aforementioned study objectives and endpoints and a rationale for the specific endpoints.

Table 5.3-1: Overview of Objectives and Endpoints

Objective	Endpoint	Rationale for Endpoint
Evaluate safety of the implant and the procedure	Safety measures peri- and post-procedure and at 14 days, 45 days, 3 months, and 12 months post index procedure	Safety assessments per society guidelines.
Evaluate effectiveness of the implant	Implant performance and other effectiveness measures peri- and post-procedure and at 14 days, 45 days, 3 months, and 12 months (if needed) post index procedure, including core laboratory review of serial imaging post implant	Effectiveness assessments per society guidelines ^{39,40} .

a: Includes computed tomography and transesophageal echocardiography and optional cardiac magnetic resonance imaging

6. Study Design

[figure not shown]
WATCHMAN FLX™ Pro CT is a prospective, single-arm, single-center, post-market investigation to assess device tissue coverage in subjects with non-valvular atrial fibrillation (AF) who receive the WATCHMAN FLX Pro device to reduce the risk of stroke. Serial advanced imaging modalities such as CT and TEE will be used. A core laboratory will independently assess select results.

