9.4. Summarization of Site-Reported Serious and Non-Serious Adverse Events

Site-reported subject-based event rates will be calculated at various time points based on all events reported by the site.

The calculation method will follow the table below and extend to other endpoints and time points (e.g., 1 year death) with the appropriate modifications to the numbers of days. For example, for 90 days, the event must have occurred within 90 days of procedure and the valid data point must be 60 days (early portion of window for the 90-day visit).

The following are the maximum days to event and number of days post-procedure that are adequate follow-up:

Follow-up Visit	Maximum Days to Event*	Days for Adequate Follow-up**
14 Days	14	11
45 Days	45	30
3 Months	90	60
1 Year	365	335

* - this is the target date for the follow-up visit except for the 1-year visit where this is the end of the visit window

** - this is the start of the visit window

All event rates will be calculated relative to the date of procedure (i.e., post-procedure).

10. Bibliography

1. WATCHMAN FLX Pro CT Protocol, 92929614 Rev/Ver C.

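### The SAP still plans for 25 subjects where the protocol now plans for 50, and the ITT wording in both documents admits screen failures to the in-hospital and device-success denominators

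*SAP*

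**What the plan says.** **Sample size and version.** The SAP's introduction says "Approximately 25 consented subjects will be enrolled", and Section 7.2.3 says "A single center may enroll up to 25 subjects". The SAP synopsis and Section 6.1 agree with these. The bibliography names the parent document as "WATCHMAN FLX Pro CT Protocol, 92929614 Rev/Ver C". Protocol Rev D, dated 08-Nov-23, raised the number to 50, and Protocol 11.2.3 now reads "A single center may enroll up to 50 subjects". On duration, the SAP has "the total study duration from first subject enrolled to last subject follow-up is estimated to be at least 17 months" and Protocol 7.1 has "the total study duration from first subject enrolled to last subject follow-up is estimated to be at least 28 months".

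**Two slips inside the SAP.** Section 5.2 times the baseline 4D MRI as "before (7 days prior to the index procedure", while the SAP synopsis says that baseline imaging, including optional MRI, "will be done within 14 days prior to the implant procedure". Section 6 calls the study post-market; the synopsis calls it premarket.

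**Analysis sets.** SAP synopsis, 5.2 and 7.2.1, and Protocol synopsis and 11.2.1, all put into ITT every subject who signs the consent form and is enrolled. Protocol 9.1 and the SAP synopsis make the signature the point of enrolment. Protocol Table 9.4-1 defines a screen failure as someone who has signed but is not clinically eligible. It leaves that person out of the enrolment ceiling and the primary analyses, and keeps Attempt subjects in both the ceiling and the endpoint analyses. The SAP does not mention screen failures.

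**Denominators.** SAP 9.3 divides in-hospital event rates by all subjects enrolled. Other outcome rates use subjects with adequate follow-up and/or an event. SAP 9.4 measures adequate follow-up in days after the procedure.

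**Precision.** Planned summaries are mean, SD, n, minimum, maximum, percentage, count and Kaplan-Meier rates. No interval is named. Both synopses say that no statistical inference will be made.

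**The concern.** Protocol 11.2 says that analyses follow the study-specific SAP. The SAP supplied describes a study half the current size, tied to a superseded protocol.

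The ITT wording matters more, because it can change reported numbers. Table 9.4-1 removes screen failures from the primary analyses only. Device success and in-hospital safety events are additional measurements, so that exclusion does not literally reach them. SAP 9.2 also makes all enrolled subjects eligible for evaluation. A programmer following the SAP as written would count screen failures in these two denominators. One who relied on Protocol 11.2.2, where eligibility appears to come before enrolment, would not. The two would produce different tables from the same data.

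Counting them understates both quantities: in-hospital event rates look better than they were, and device success looks worse.

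**Working it through.** **1. Plan figures.** Neither 25 nor 50 has a derivation; Protocol 11.1.1 says that sample size estimates do not apply. No alpha, power or event count is therefore affected.

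Duration is enrolment plus follow-up:
- SAP: 5 + 12 = 17 months, which matches its figure.
- Protocol: 15 + 12 = 27 months, one short of the stated 28. Adding the 30-day window of the 12-month visit gives 15 months + 395 days, or about 28.0 months. On that convention the SAP total would be about 18.0, so the two totals use different conventions.

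**2. Does a screen failure meet the ITT definition?** ITT requires a signature and enrolment. Enrolment is the signature. A screen failure has signed. So yes, as written in both documents.

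**3. Which rates does this reach?**
- In-hospital event rates: reached, because SAP 9.3 divides by everyone enrolled.
- Device success on the ITT basis: reached, because no narrower denominator is given.
- Post-discharge rates: not reached. SAP 9.3 requires discharge after the index procedure, plus adequate follow-up or the event.
- Kaplan-Meier and fixed-time rates: not reached. SAP 9.3 and 9.4 count time from the procedure date. A screen failure has none and exits on being found ineligible.

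**4. Size.** Rate = x / (50 + s), where s is the number of screen failures. The documents give no value for s, so 0, 5 and 10 are assumptions. So are 50 successes and 2 in-hospital events.

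| s | Device success | In-hospital events |
|---|---|---|
| 0 | 50/50 = 100% | 2/50 = 4.0% |
| 5 | 50/55 = 90.9% | 2/55 = 3.6% |
| 10 | 50/60 = 83.3% | 2/60 = 3.3% |

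**5. What an interval would show (exact two-sided 95%, Clopper-Pearson).** With zero events the upper limit is 1 − 0.025^(1/n): 7.1% at n = 50 and 13.7% at n = 25. For 2/50 the interval is 0.5% to 13.7%. For 50/50 the lower limit is 92.9%.

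For a Kaplan-Meier rate with 2 events in 50 and no censoring, S = (49/50)(48/49) = 0.96, so the event rate is 4.0%. The Greenwood variance is 0.96² × [1/(50×49) + 1/(49×48)] = 0.000768, so SE = 2.77 percentage points. The untransformed interval is 4.0 ± 1.96 × 2.77, or −1.4% to 9.4%. The log-log interval is 1.0% to 15.1%. Since the plain interval falls below zero, the transformation should be named if intervals are added.

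**The case against.** **The version lag is administrative.** The SAP's revision entry is dated 27-Mar-2023, before Rev D, and SAP 7.3 already allows amendment before analysis. No method depends on 25 subjects or 17 months. All of this stands. A reader might infer that the analysis would be cut off at 25 subjects, but nothing in the SAP does that. The duration, MRI-window and post-market items are clerical.

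**Screen failures may be few, and the intent is visible.** Eligibility is assessed from standard of care. Both synopses describe the target cohort as subjects in whom implantation is attempted, and Protocol 11.2.2 and Table 9.4-1 point towards exclusion. This makes exclusion the likelier intention, but the rule as written still includes them.

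**The reach is narrow.** A reader might infer that every ITT rate, including the 12-month safety rates, is diluted. SAP 9.3 and 9.4 do not support that, for the reasons in step 3.

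**The SAP is not the sole source.** A reader might infer that the ITT problem comes from the missed update. It does not: protocol Rev D uses the same ITT wording, so alignment alone would leave it in place.

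**Leaving out intervals is consistent with a descriptive study.** This stands. A reader might call it a contradiction or an error. It is neither: readers can rebuild a binomial interval from a reported count and denominator, and the list in SAP 7.1 is given as examples. They cannot rebuild an interval from a censored Kaplan-Meier rate alone.

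**Conclusion.** The point holds in two parts. First, the supplied SAP states the wrong maximum sample size and cites a superseded protocol. That is a factual correction with no effect on who is analysed. Only this SAP revision was available, so a later amendment cannot be excluded.

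Second, the ITT definition shared by both documents, read with enrolment at signature, admits screen failures to two quantities: in-hospital event rates and ITT device success. If there are 5 or 10 screen failures, device success falls by 9.1 or 16.7 percentage points from 100%, and two in-hospital events move from 4.0% to 3.6% or 3.3%. With none, nothing changes.

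A related gap is that a consented, eligible subject in whom no access sheath is inserted has no class in Table 9.4-1. One example is a subject found to have thrombus on baseline imaging, for whom Protocol 10.4 says that implantation is not attempted. Such a subject also meets the ITT wording.

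The absence of intervals is a reporting gap that can be filled cheaply. The matter should be fixed before analysis; it does not threaten the study.

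**What to change.** Before analysis:

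1. Amend the SAP to protocol Rev D: up to 50 subjects, the current duration (checking the 27 versus 28 months), the protocol reference, the 14-day baseline MRI window and the premarket description.
2. In SAP 7.2.1 and 9.3, and in Protocol 11.2.1 and both synopses, state that screen failures are excluded from ITT and from the in-hospital denominator, and that Attempt subjects stay in. State how consented, eligible subjects with no implant attempt are classed and whether they count.
3. Optionally, add exact 95% intervals for key proportions such as device success, and log-log intervals for Kaplan-Meier rates. Label them descriptive, with no hypothesis test, and clarify the no-inference sentence in both documents to match.

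The cost is one SAP amendment, a few lines in the protocol (which Protocol 15.3 sends to the ethics committee) and, for item 3, some extra table columns. No new data are needed. The downside of item 3 is that rates look less favourable with their intervals beside them.
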